6.5.1 Rescue Medication

All subjects will be prescribed an epinephrine auto-injector to have available for rescue at home. All subjects will also be prescribed an oral antihistamine, cetirizine, to have available for rescue at home. It will be confirmed that all subjects with an underlying diagnosis of asthma have a prescription for a short acting beta-agonist (albuterol or levalbuterol) available for rescue at home. Any subjects with a diagnosis of asthma that do not have a short acting beta-agonist will have one prescribed.

The study sites (Pediatric Allergy office and Clinical Research Unit) will have rescue medications available at the time of each study visit. The following rescue medications may be used:

Treatment	Adult Dose	Route	Dosing Interval	Special Considerations	Pediatric Dose
EPINEPHRINE IM/SQ	1:1000 concentration 0.3mg (range 0.3-0.5mg, maximum 1mg per dose)	IM vastus lateralis (lateral thigh) is recommended site for quickest absorption. Can also be given SQ or IM in deltoid.	Every 5 to 10 minutes prn or sooner if clinician deems appropriate	
 Give as soon as diagnosis of anaphylaxis is suspected 	1:1000 concentration 0.01mg/kg OR 0.15mg pediatric autoinjectable (maximum 0.5mg/mg per dose)
PATIENT POSITION				
 Place patient in supine position and elevate lower extremities when there is concern for hemodynamic compromise. 	
OXYGEN	Consider 8-10 L/min initially, may titrate using pulse oximetry as guide	Appropriate to patient condition –i.e. nasal canula or mask		
 Especially appropriate for prolonged and severe reactions 	Titrated using pulse oximetry as guide
INTRAVENOUS FLUIDS	Crystallloid Solution, preferably normal saline (NS) 1 to 2 liters bolus	Intravenous	5-10 ml/kg in the first 5 minutes. Colloid solution: 500 ml rapidly, followed by slow infusion.	
 Caution for volume overload, advised for patients with history of CHF Intraosseous access infusion can be used if IV access is unsuccessful (must use infusion pump, pressure bag, or manual pressure to overcome venous resistance) 	20-30 ml/kg in the first hour
INHALED β_2 ADRENERGIC AGONISTS	Albuterol sulfate 2.5 mg/3ml unit dose or Xopenex (levalbuterol HCl) 1.25 mg/3ml unit dose	Per Nebulizer via mouth-piece or mask as tolerated.	Delivered over 5-15 minutes and continued as necessary for bronchospasm	
 Used when bronchospasm does not respond to epinephrine 	0.15 mg/kg (minimum dose 2.5 mg) every 20 minutes for 3 doses then 0.15-0.3 mg/kg (not to exceed 10 mg) every 1-4 hours as needed or 0.5 mg/kg/hour by continuous nebulization
GLUCAGON	1 to 5 mg IV over 5 minutes	Intravenous (Glucagon administered as IV push should be reconstituted with 1 ml sterile water for injection or sterile water for reconstitution)	If no response following IVP consider IV infusion, 0.05-0.1 mg/kg/h OR 1 – 5 mg/hr titrated to clinical response	
 Used if epinephrine is not effective in patients taking β-blockers (may reverse refractory bronchospasm and hypotension) Iosotonic volume expansion may also be necessary (in some cases up to 7 L) Protection of the airway is important since glucagon can cause vomiting and risk aspiration (place in lateral recumbent position to protect airway) 	20-30 μ g/kg IV x1 (maximum 1 mg)
EPINEPHRINE IV	1:100,000 solution (0.1 mg [1 ml of 1:1000] in 100 ml saline)	Intravenous	Initial rate of 30-100 ml/hr (3-15 μ g/min) per infusion pump, titrate for hemodynamic response	
 Used in patients with poor response to IM/SQ Epinephrine Used only in profoundly hypotensive patients not responding to IV volume replacement. Every minute VS and EKG monitoring should be considered 	0.1 μ g/kg/min [0.6 X body weight (in kg) = # of mg diluted to total 100 ml saline; then 1 ml/h delivers 0.1 μ g/kg/min]
VASOPRESSOR	Dopamine (400 mg in 500 ml of 5% Dextrose)	Intravenous	2-20 μ g/kg/min, titrated to maintain systolic > 90 mm Hg	
 Used if epinephrine and volume expansion fail to alleviate hypotension. Transfer to hospital ASAP 	2-20 μ g/kg/min [6 X body weight (in kg) = # of mg diluted to total 100 ml saline; then 1 ml/h delivers 1 μ g/kg/min]

Cetirizine 10 mg	Oral	2.5-10 mg
-------------------------	-------------	------------------

H2 ANTIHISTAMINE	Famotidine (Pepcid) 20 mg or ranitidine 1mg/kg (max 30mg)	hypotension)	Intravenous (10 mg/ml, undiluted)	Administer each 20 mg or fraction thereof over at least 2 minutes IV push	
 Side effects: headache, dizziness, constipation, diarrhea. Confusion increased in patients > 50 years old; thought to be associated with renal or hepatic impairment 	0.25 - 0.5 mg/kg (maximum dose 40 mg/day)
CORTICO-STEROID	Methylprednisolone sodium succinate (solumedrol) IV – 40-125mg, q 4-6 hours; Status asthmaticus – 0.5-1mg/kg q6 hours	IV push Oral can be considered for risk of biphasic reaction, data inconclusive, doses vary	IV push doses administered over 2 to 3 minutes		
 Not effective for acute treatment of anaphylaxis, but may prevent protracted anaphylaxis No conclusive evidence for prevention of biphasic response 	Children <12 years 0.5 – 1.7 mg/kg/day divided q6 – 12h. Status asthmaticus – 0.5-1mg/kg q6 hours

7. Study Intervention Discontinuation and Participant Discontinuation/Withdrawal

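### The adult IV epinephrine entry in the rescue table gives 0.1 mg where its own ratio label and stock volume give 1 mg; the rate and dose ranges in that row disagree, and the paediatric IM maximum carries an impossible unit

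*Protocol*

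**What the plan says.** Protocol section 6.5.1 lists the rescue medications that may be used at the two study sites, the Pediatric Allergy office and the Clinical Research Unit. It has separate adult and paediatric dose columns.

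- **Adult IV epinephrine, preparation:** "1:100,000 solution (0.1 mg [1 ml of 1:1000] in 100 ml saline". This describes one bag in three ways: a ratio label, a mass and a stock volume.
- **Adult IV epinephrine, rate:** "Initial rate of 30-100 ml/hr (3-15 μ g/min) per infusion pump, titrate for hemodynamic response".
- **When the row applies:** "Used only in profoundly hypotensive patients not responding to IV volume replacement".
- **Paediatric IV epinephrine:** 0.1 µg/kg/min, prepared as "0.6 X body weight (in kg) = # of mg diluted to total 100 ml saline", with 1 ml/h said to deliver that dose.
- **IM epinephrine:** the adult cell reads "1:1000 concentration 0.3mg (range 0.3-0.5mg, maximum 1mg per dose". The paediatric cell gives 0.01 mg/kg with a "maximum 0.5mg/mg per dose".

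Enrolment covers ages 1 to 16 (Protocol section 5.1). The epinephrine rows give no age or weight at which a participant moves from the paediatric to the adult column. Neither the SAP nor the protocol's summary of changes corrects these cells.

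**The concern.** Three descriptions of the same bag should give the same concentration, and these do not. The protocol deliberately exposes peanut-allergic children to roasted peanut at two food challenges and to repeated supervised up-dosing with boiled peanut, so the rescue table is an operative instruction.

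The epinephrine infusion is reached only after IM or SQ epinephrine and fluid have failed. If a larger adolescent were dosed from the adult column and staff worked from the stated mass, the infusion would start from a bag at one tenth of its labelled strength, at the point where delay costs most.

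The mismatch between pump rate and dose in the same row, and the malformed unit on the IM cap, are smaller faults. They sit in the same two epinephrine rows and can be corrected together.

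**Working it through.** All inputs come from the epinephrine rows of Protocol section 6.5.1, except the adolescent body weight in step 4, which is assumed.

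**1. Bag strength.** A ratio of 1:x means 1 g in x ml, or 1,000,000/x µg/ml.

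- Ratio label: 1:100,000 = 10 µg/ml.
- Stock volume: 1:1000 = 1000 µg/ml = 1 mg/ml, so 1 ml holds 1 mg. In 100 ml that is 1000/100 = 10 µg/ml, which reproduces the label.
- Stated mass: 0.1 mg in 100 ml = 100/100 = 1 µg/ml, or 1:1,000,000. This does not reproduce the label.

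Two alternative readings do not rescue the 0.1 mg. Adding 1 ml to 100 ml gives 101 ml and 9.9 µg/ml (1:101,000), a trivial change. A 1:10,000 stock would hold 0.1 mg per ml, but the cell specifies 1:1000, and a bag made that way would still be 1:1,000,000 and fail its label.

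**2. Rate against dose.** Delivery (µg/min) = ml/hr × µg/ml ÷ 60.

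| Bag | At 30 ml/hr | At 100 ml/hr | Compared with the stated 3-15 µg/min |
|---|---|---|---|
| 10 µg/ml (label, stock volume) | 30 × 10/60 = 5.0 | 100 × 10/60 = 16.7 | 5/3 = 1.7 and 16.7/15 = 1.1 times the stated ends |
| 1 µg/ml (stated mass) | 30 × 1/60 = 0.5 | 100 × 1/60 = 1.67 | 3/0.5 = 6 and 15/1.67 = 9 times too low |

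The 10 µg/ml bag comes close to the stated dose range and the 1 µg/ml bag does not, which is further evidence that 1 mg was meant. No single strength fits both ends exactly: the low end needs 3 × 60/30 = 6 µg/ml and the high end 15 × 60/100 = 9 µg/ml. At 10 µg/ml, 3-15 µg/min corresponds to 3 × 60/10 = 18 to 15 × 60/10 = 90 ml/hr.

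**3. Paediatric IV recipe.** 0.6 × kg mg in 100 ml is 6 × kg µg/ml. At 1 ml/h that is 6 × kg/60 = 0.1 × kg µg/min, or 0.1 µg/kg/min. For example, at 20 kg: 12 mg in 100 ml = 120 µg/ml; 120/60 = 2 µg/min; 2/20 = 0.1 µg/kg/min. The recipe is correct as written.

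**4. What the tenfold error would mean for an adolescent.** Assume 50 kg (range 40-60 kg).

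- The paediatric dose of 0.1 µg/kg/min is 5 µg/min (4-6). At 10 µg/ml that is 5 × 60/10 = 30 ml/hr (24-36).
- The 0.1 mg bag at 30-100 ml/hr would give 0.5/50 = 0.01 to 1.67/50 = 0.033 µg/kg/min.

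**5. IM cap.** The parallel adult cell expresses its maximum in mg per dose, so 0.5 mg per dose is the natural reading of the paediatric one. At 0.01 mg/kg that cap binds only above 0.5/0.01 = 50 kg.

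**The case against.** The arithmetic is not in dispute. The case on the other side is about reach.

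- Every participant is aged 1 to 16, the table has a paediatric column, and the paediatric IV recipe is right. Harm requires an adolescent to be dosed from the adult column, a route the protocol never states.
- Two of the three bag descriptions are correct, including the volume to draw up, so staff would have to overlook both to make the wrong bag.
- The error is an under-dose in an infusion that is titrated to response, run by physicians trained to treat these reactions, in a trial of 10 children that excludes a history of life-threatening peanut anaphylaxis.
- The rate mismatch is modest, the documents do not show which range is wrong, and mg/mg is plainly a slip.

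Most of this stands, and it sets the level of concern. The rate point can be put only as two ranges that disagree, and the IM unit is editorial. The adult-column argument is not complete, however. Ages run to 16, and the epinephrine rows set no boundary between the columns. The only age cut-off in the table's dosing cells is in the corticosteroid row (under 12 years), and a clinician who borrowed it would dose ages 12 to 16 as adults. Titration and an alert reader make harm less likely, but an emergency recipe should not depend on either.

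**Conclusion.** The concern holds and should be fixed. The 0.1 mg in the adult IV epinephrine cell is wrong by a factor of 10 against its own ratio label and stock volume. A bag made from it would deliver 6 to 9 times less than the dose range stated in the same row. At the correct strength, the stated rate still overshoots the stated dose by 1.7 times at the low end and 1.1 times at the high end. The unit of the paediatric IM maximum is malformed, with little practical consequence.

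The bag-strength conclusion rests only on figures in the cell. The clinical consequence rests on two assumptions: that a participant is dosed from the adult column, and that the bag is made from the stated mass. Neither is likely, so this is a cheap safety correction and not a flaw in the design. It has no bearing on the endpoints, sample size or analysis.

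**What to change.** Make three corrections in the two epinephrine rows of Protocol section 6.5.1:

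1. Adult IV preparation: replace 0.1 mg with 1 mg, keeping the 1:100,000 label, the 1 ml of 1:1000 stock and the 100 ml saline.
2. Adult IV rate: make the two ranges agree, either 18-90 ml/hr for 3-15 µg/min or 30-100 ml/hr for 5-16.7 µg/min. The choice is clinical.
3. Paediatric IM maximum: write 0.5 mg per dose.

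Leave the paediatric IV recipe as it is. The medical lead and the pharmacy should sign off the corrected cells, and the corrected table should go to both the Pediatric Allergy office and the Clinical Research Unit, replacing any copies in use. The cost is one short amendment and the reissue, with no change to design, sample size or analysis.

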7.1 Discontinuation of Study Intervention

Criteria for discontinuing oral immunotherapy in a subject will include:

- Subject nonadherence to OIT, specifically defined by 12 (approximately 10%) nonconsecutive missed doses.
- A life-threatening adverse reaction to OIT, specifically a grade 4 reaction as defined by the Consortium of Food Allergy Research (CoFAR) criteria. See table in Section 8.3.3.1.
- Symptoms suggestive of Eosinophilic Esophagitis (EoE) – i.e. difficulty swallowing, chest pain, persistent heart burn, upper abdominal pain, and/or no response to gastroesophageal reflux disease (GERD) medication

Symptoms suggestive of Eosinophilic Esophagitis (EoE) will prompt discontinuation of oral immunotherapy and begin once weekly symptom monitoring phone calls with study staff. If symptoms fail to resolve after 1 month off therapy, consultation with Gastroenterology will be considered for further evaluation and management.

Discontinuation from oral immunotherapy does not mean discontinuation from the study, and remaining study procedures should be completed as indicated by the study protocol. If a clinically significant finding is identified (including, but not limited to changes from baseline) after enrollment, the investigator or qualified designee will determine if any change in participant management is needed. Any new clinically relevant finding will be reported as an adverse event (AE).

The data to be collected at the time of study intervention discontinuation will include the following:

- Skin prick test to peanut
- Peanut sIgE, peanut component panel, and peanut IgG4

7.2 Participant Discontinuation/Withdrawal from the Study

Participants are free to withdraw from participation in the study at any time upon request. Subjects may withdraw from the study for the following anticipated reasons

- Adverse events related to OIT
 - Chronic or recurrent GI symptoms
 - Acute hypersensitivity reactions
 - Chronic or recurrent cutaneous symptoms
- Social reasons: time constraints, transport
- Principal Investigator temporarily suspends or prematurely discontinues study participation. The date and reason for discontinuation must be documented (e.g. non-compliance). Every effort should be made to complete the appropriate assessments.
- Pregnancy during the course of the study for a child-bearing participant
- The investigator considers it, for safety reasons, to be in the best interest of the subject.
- Disease progression
 - Worsening asthma that requires increasing therapy such that exclusion criteria are met

The reason for subject discontinuation or withdrawal from the study will be recorded on the Case Report Form (CRF). Subjects who sign the informed consent form and are enrolled but do not receive the study intervention may be replaced. Subjects who sign the informed consent form, and are enrolled and receive the study intervention, and subsequently withdraw, or are withdrawn or discontinued from the study, will not be replaced.

7.3 Lost to Follow-up

A participant will be considered lost to follow-up if he or she fails to return for 2 scheduled visits and is unable to be contacted by the study site staff.

The following actions must be taken if a participant fails to return to the clinic for a required study visit:

- The site will attempt to contact the participant and reschedule the missed visit within 1 week for an updosing visit or within 1 month for a follow up visit and counsel the participant on the importance of maintaining the assigned visit schedule and ascertain if the participant wishes to and/or should continue in the study.
- Before a participant is deemed lost to follow-up, the investigator or designee will make every effort to regain contact with the participant (where possible, 3 telephone calls and, if necessary, a certified letter to the participant's last known mailing address or local equivalent methods). These contact attempts should be documented in the participant's medical record or study file.
- Should the participant continue to be unreachable, he or she will be considered to have withdrawn from the study with a primary reason of lost to follow-up.

8. Study Assessments and Procedures

8.1 Efficacy Assessments

Procedures

Skin tests: Skin testing to peanut will be performed at the visits specified in the SoA (section 1.3). Skin testing will include skin prick with peanut exact (1:20 w/v, Greer), negative control (saline) and positive control (histamine).

Laboratory tests: Blood samples will be collected at the visits specified in the SoA. Blood work will include peanut specific IgE concentration, peanut component testing (peanut specific IgE concentration for Ara h 1, 2, 3, 8 and 9), and peanut specific IgG4 concentration. The peanut sIgE and peanut component panel will be sent to the Cleveland Clinic main laboratory. The peanut specific IgG4 will be sent to Mayo Clinic laboratories. The laboratories used will supply a list of reference ranges and units of the laboratory parameters.

Volume of blood to be collected:

Peanut specific IgE concentration	0.5 mL
Peanut component panel	0.6 mL
Peanut IgG4 concentration	0.5 mL
Total	1.6 mL

8.2 Safety and Other Assessments

Screening to ensure all subjects meet the inclusion criteria and do not meet any exclusion criteria will be performed within 1 month of the initial oral food challenge visit. At Visit 1, the physician and participant will review and update the patient's Food Allergy & Anaphylaxis Emergency Care Plan. This plan will outline the recommended treatment in case of an allergic reaction occurs during their enrollment in the study. This plan is signed by a physician, and includes emergency contact information. In addition, each study visit will include obtaining a brief interim history to ensure that no potential augmenting factors, such as viral illness, are present at the time of study drug or control drug administration. Vital signs, a targeted physical exam and conmed review will be performed prior to any study drug administration for the same purposes.

Study visit evaluation:

Brief interim history

Discussion of any interim AEs

Vital signs: Temperature, Heart Rate, Respiratory Rate

Physical Exam: Targeted assessment of General Appearance, HEENT, Cardiac, Respiratory, Abdominal, and Skin

8.3 Adverse Events and Serious Adverse Events

8.3.1 Definition of Adverse Event

Adverse event means any untoward medical occurrence associated with the use of an intervention in humans, whether or not considered intervention-related (21 CFR 312.32 (a)).

The CoFAR (the consortium of Food Allergy research) scale will be referenced to assess SAEs/AEs related or possibly related to an allergic reaction. CTCAE (Common Terminology Criteria for Adverse Events) version 5.0 will be referenced for SAEs/AEs that are not related to allergic reactions and are therefore not listed in the CoFAR scale.

8.3.2 Definition of Serious Adverse Events (SAE)

An adverse event (AE) or suspected adverse reaction is considered "serious" if, in the view of either the investigator or sponsor, it results in any of the following outcomes: death, a life-threatening adverse event, inpatient hospitalization or prolongation of existing hospitalization, a persistent or significant incapacity or substantial disruption of the ability to conduct normal life functions, or a congenital anomaly/birth defect. Important medical events that may not result in death, be life-threatening, or require hospitalization may be considered serious when, based upon appropriate medical judgment, they may jeopardize the participant and may require medical or surgical intervention to prevent one of the outcomes listed in this definition. Examples of such medical events include allergic bronchospasm requiring intensive treatment in an emergency room or at home or hypotension not responsive to treatment with epinephrine.

8.3.3 Classification of an Adverse Event

8.3.3.1 Severity of an Event

All adverse events will be graded in severity utilizing criteria specifically developed by the Consortium of Food Allergy Research.²⁷ These criteria are widely accepted and applied to OIT clinical trials.

Grade 1 Mild	Grade 2 Moderate	Grade 3 Severe	Grade 4 Life threatening	Grade 5 Death
Transient or mild discomforts (< 48 hours), no or minimal medical intervention/therapy required. These symptoms may include pruritus, swelling or rash, abdominal discomfort or other transient symptoms.	Symptoms that produce mild-to-moderate limitation in activity, some assistance may be needed; no or minimal intervention/therapy is required. Hospitalization is possible. These symptoms may include persistent hives, wheezing without dyspnea, abdominal discomfort/increased vomiting or other symptoms.	Marked limitation in activity, some assistance usually required; medical intervention/therapy required, hospitalization is possible. Symptoms may include bronchospasm with dyspnea, severe abdominal pain, throat tightness with hoarseness, and transient hypotension among others. Parenteral medication(s) are usually indicated.	Extreme limitation in activity, significant assistance required; significant medical/therapy. Intervention is required; hospitalization is probable. Symptoms may include persistent hypotension and/or hypoxia with resultant decreased level of consciousness associated with collapse and/or incontinence or other life-threatening symptoms	Death

8.3.3.2 Relationship to Study Intervention

All adverse events (AEs) must have their relationship to study intervention assessed by the clinician who examines and evaluates the participant based on temporal relationship and his/her clinical judgment.

The degree of certainty about causality will be graded using the categories below. In a clinical trial, the study product must always be suspect.

- **Definitely Related** – There is clear evidence to suggest a causal relationship, and other possible contributing factors can be ruled out. The clinical event, including an abnormal laboratory test result, occurs in a plausible time relationship to study intervention administration and cannot be explained by concurrent disease or other drugs or chemicals. The response to withdrawal of the study intervention (dechallenge) should be clinically plausible. The event must be pharmacologically or phenomenologically definitive, with use of a satisfactory rechallenge procedure if necessary.
- **Probably Related** – There is evidence to suggest a causal relationship, and the influence of other factors is unlikely. The clinical event, including an abnormal laboratory test result, occurs within a reasonable time after administration of the study intervention, is unlikely to be attributed to concurrent disease or other drugs or chemicals, and follows a clinically reasonable response on withdrawal (dechallenge). Rechallenge information is not required to fulfill this definition.
- **Potentially Related** – There is some evidence to suggest a causal relationship (e.g., the event occurred within a reasonable time after administration of the trial medication). However, other factors may have contributed to the event (e.g., the participant's clinical condition, other concomitant events). Although an AE may rate only as "possibly related" soon after discovery, it can be flagged as requiring more information and later be upgraded to "probably related" or "definitely related", as appropriate.
- **Unlikely to be related** – A clinical event, including an abnormal laboratory test result, whose temporal relationship to study intervention administration makes a causal relationship improbable (e.g., the event did not occur within a reasonable time after administration of the study intervention) and in which other drugs or chemicals or underlying disease provides plausible explanations (e.g., the participant's clinical condition, other concomitant treatments).
- **Not Related** – The AE is completely independent of study intervention administration, and/or evidence exists that the event is definitely related to another etiology. There must be an alternative, definitive etiology documented by the clinician

